## **Aim**

The primary aim of this randomized controlled trial was to investigate the effects of an 8-week home-based physiotherapeutic foot-ankle exercise program using an educational booklet on DPN symptoms and severity. The secondary goal was to investigate the effects of this intervention at 8 and 16 weeks on tactile and vibration sensitivities, foot health and functionality, foot muscle strength, functional balance, plantar pressure, foot-ankle kinematics, and lower limbs kinematics and kinetics during gait.

## **Methods/Design**

### **Study design and data collection**

This trial is designed as a single-blind, two-parallel arms RCT, wherein patients with DPN will be randomly allocated to either a control group (CG) or an intervention group (IG). This trial protocol follows all recommendations established by SPIRIT (2013) [47], has been approved by a research ethics committee (CAAE: 90331718.4.0000.0065), and was registered at ClinicalTrials.gov on July 2, 2019 (identifier NCT04008745).

Patients in the CG will not receive any specific intervention beyond the usual care, including treatment recommended by the medical team, pharmacological treatment, self-care guidelines, and a weekly telephone call to check on the adherence to care, which will be maintained in both groups [48]. Patients in the IG will perform a foot-related exercise program included in an educational booklet three times/week at home for 8 weeks. After 8 weeks, IG

participants will be encouraged to continue this exercise until the end of the study following the same schedule set in the intervention period. If proven effective, the benefits of the foot-related exercises protocol will be explained and offered to all control participants at the end of the study.

Patients from both groups will be evaluated for all outcomes at baseline (T0), 8 weeks (T8, end of intervention), and 16 weeks (T16, follow-up). All procedures in this study will follow the norms of the Operational Procedure Manual developed specifically for this research. The design and flowchart following the Consolidated Standards of Reporting Trials (CONSORT) guidelines [49] are presented in Fig. 1.

[figure not shown]

Figure 1 - Consolidated Standards of Reporting Trials (CONSORT) flow diagram illustrating the process of FOCA-II.

## **Study Setting**

The participants allocated to the IG will be treated at their homes, but the first session will take place at the outpatient clinic of the Laboratory of Biomechanics of Human Movement and Posture (LaBiMPH). This clinic is located at the Physical Therapy, Speech and Occupational Therapy department of the School of Medicine of the University of São Paulo and assists all the physical therapy treatments of the laboratory, providing a reliable therapeutic environment for the first intervention. All assessments will be performed at the same laboratory.

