### **Treatment arms**

#### **Control**

CG patients will not receive any specific intervention other than the treatment recommended by the health care team, which will include pharmacological treatment and self-care guidelines following the International Working Group on the Diabetic Foot guide [52]. These self-care guidelines have been adjusted for our setting in Sao Paulo and include (1) instructing patients to inspect their feet and inside of shoes daily, wash feet daily (with careful drying, particularly between toes), avoid using chemical agents or plasters to remove calluses or corns, avoid cutting calluses or blisters without supervision, use emollients to lubricate dry skin, and cut toe nails straight across; (2) instructing patients to use socks without elastic and sewing; (3) instructing patients to avoid walking barefoot or wearing shoes without socks or slippers and to seek medical assistance whenever identifying problems in their feet; and (4) providing education

aimed at improving footcare knowledge and behavior as well as encouraging the patient to adhere to this footcare advice. These guidelines will be maintained for both groups. Patients in this group will also receive a weekly telephone call to check the adherence to the care recommended by the medical staff and the foot care guidelines and to avoid the nocebo effect.

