### **Outcomes and measures**

Two researchers (Researchers #4 and #5) who are blinded to group allocation will perform all assessments. Participants of both groups will be assessed at baseline (T0), at the end of intervention (T8, 8 weeks after baseline), and at follow-up (T16, 16 weeks after baseline). Table 1 shows the schedule of enrollment, intervention, and assessments according to the SPIRIT guidelines [47].

Table 1 - Schedule of enrollment, intervention, and assessments of the FOCAtrial-II, following SPIRIT guideline

TIMEPOINT	Enrollment	Allocation	Post-allocation	Follow-up	
	T-1	T0	T0	T8	T16
Eligibility screen	X				
Informed consent	X				
Allocation			X		
INTERVENTIONS					
Intervention Group					
Control Group					
ASSESSMENTS					
DPN symptoms		X	X	X	
Fuzzy classification of the DPN severity		X	X	X	
Foot- ankle kinematics and kinetics during gait		X	X	X	
Dynamic plantar pressure distribution during gait		X	X	X	
Tactile sensitivity		X	X	X	
Vibration sensitivity		X	X	X	
Foot health and functionality		X	X	X	
Foot isometric strength		X	X	X	
Functional balance		X	X	X	

An initial anamnesis will be performed to check the eligibility criteria, including clinical, anthropometric, and demographic characteristics of all participants. The classification of DPN severity will be made using the fuzzy score from a web software program [13,53]. Participants with scores equal to or above 2.0, corresponding to mild DPN, will be included in the study. Those who score between 12 and 21 (probable depression) on the Brazilian-Portuguese HADS will not be included [54].

The DPN symptoms and the classification of the DPN severity will be the primary

outcomes. The foot-ankle kinematics and kinetics during gait, plantar pressure distribution during gait, tactile and vibration sensitivities, foot health and functionality, foot strength, and functional balance will be the secondary outcomes.

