### **DPN symptoms**

Patients will answer the Brazilian version of the Michigan Neuropathy Screening Instrument (MNSI) [55]. This questionnaire has 15 questions about the sensitivity of the feet and legs and is self-administered. A score of 1 point is given for answers of “yes” for questions 1, 2, 3, 5, 6, 8, 9, 11, 12, 14, and 15 and “no” for questions 7 and 13. Questions 4 and 10 evaluate circulatory deficits and general asthenia, respectively, and neither are included in the final score. The sum of all scores ranges from 0 to 13, and the larger the score, the worse the DPN.

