### **Statistical Analysis Plan**

The sample size was calculated using the GPower v. 3.1 program [64] based on the following outcomes: MNSI DPN symptoms (primary) and ankle sagittal ROM during gait (secondary). These two outcomes were chosen because they reflect important functional gains for DPN patients. Thus, two sample size calculations were performed, and we selected the one that resulted in the largest number of participants. The effect sizes used for both calculations were based on a study that evaluated the effect of 12 weeks of supervised foot exercise in DM patients [34]. In that study, the improvement in the MNSI symptoms had a medium effect size

(0.52), as did gains in the ankle sagittal ROM during gait (0.46). We chose to use half of the effect size obtained in [34] because the nature of our intervention is home based, whereas Sartor's was face-to-face, which is assumed to be more effective.

The input factors for sample size calculation were a statistical design of F-test with interaction between and within factors with two repeated measures and two study groups, statistical power of 0.80, alpha of 0.05, and effect sizes of 0.26 (MNSI symptoms) and 0.23 (ankle ROM). The resulting sample sizes were 32 and 40 individuals for MNSI and ROM outcomes, respectively. Therefore, we defined our sample size as 40. Assuming a 20% dropout rate during the study, a sample size of 48 patients is needed.

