Inferential statistical analyses will be conducted using intention-to-treat and per protocol analyses. The missing data will be treated by imputation methods depending on the type: missing completely at random, missing at random, or not at random [65]. The per-protocol analysis will include only those patients who complete follow-up in the allocated intervention group. Confirmation of normality (Kolmogorov–Smirnov test), homoscedasticity (Levene test), and imputation of the means for the missing data of variables with normal distribution will be conducted. After that, mixed general linear models of analysis of variance for repeated measures will be used to detect treatment–time interactions, followed by Newman–Keuls post hoc test to obtain group effect (intervention and control), time effect (between T0, T8, and T16), and group–time interaction. Significant differences will be considered at  $\alpha = 5\%$ , but for the description of the effect of the intervention, the effect size (Cohen coefficient) and difference between the means will be calculated with their respective 95% confidence intervals.

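### A patient who stays in the trial but misses the T8 or T16 laboratory visit has no MNSI value, although this primary outcome is a self-completed form that could be sent home

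*Combined protocol and SAP*

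**What the plan says.** Study Setting allows no exception on place: "All assessments will be performed at the same laboratory". Outcomes and measures allows none on personnel: "Two researchers (Researchers #4 and #5) who are blinded to group allocation will perform all assessments". Study design and data collection fixes the time points: "Patients from both groups will be evaluated for all outcomes at baseline (T0), 8 weeks (T8, end of intervention), and 16 weeks (T16, follow-up").

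On the outcome itself, Outcomes and measures says "The DPN symptoms and the classification of the DPN severity will be the primary" outcomes. DPN symptoms are measured by the MNSI, of which its own section says "This questionnaire has 15 questions about the sensitivity of the feet and legs and is self-administered".

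On missing values, the Statistical Analysis Plan says "Assuming a 20% dropout rate during the study, a sample size of 48 patients is needed". It commits to intention-to-treat and per-protocol analyses, refers to imputation methods chosen by missingness type, and names one method: "imputation of the means for the missing data of variables with normal distribution will be conducted".

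Both arms are telephoned weekly. The Control section says "Patients in this group will also receive a weekly telephone call", and the blinding section gives the intervention-monitoring calls to Researcher #3, who knows the allocation. These calls concern adherence, not outcome collection. No section describes a mailed, electronic or other route for the MNSI.

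**The concern.** Gait capture, plantar pressure, toe strength and the sensory tests need the laboratory. As described, the MNSI does not: the patient answers 15 questions, and 13 of them are summed to a 0–13 score. Tying it to the same visit means that anyone who skips that session also loses a primary value that they could have given from home.

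Patients know their arm, so attendance may be related to symptoms or to allocation. Mean imputation, the one method named, carries no information about the individual who was absent. A returned form does. At stake is how much of the MNSI comparison rests on observed values.

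**Working it through.** **Inputs from the SAP.** f = 0.26 (MNSI) and 0.23 (ankle ROM), alpha 0.05, power 0.80, two groups, two repeated measures, 20% dropout, N = 48. The within-patient correlation ρ is not given, so 0.5 is assumed and then varied.

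**Step 1: reproduce the plan's figures.** For the group-by-time interaction, λ = f²·N·m/(1−ρ), with m = 2 and df 1 and N−2.
- MNSI, N = 32: λ = 0.0676 × 32 × 2/0.5 = 8.65, power 0.81.
- ROM, N = 40: λ = 0.0529 × 40 × 2/0.5 = 8.46, power 0.81.

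These are the smallest even totals that reach 0.80, and they match the stated 32 and 40. So ρ = 0.5 is consistent with the plan.

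**Step 2: values at risk.** 48 × 0.20 = 9.6 patients, leaving 38.4. If all of them are lost before T8, up to 2 × 9.6 = 19.2 MNSI values are missing over T8 and T16.

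**Step 3: effect of returned forms on precision.** The return share r is assumed, since the documents give none. Patients with data: n = 38.4 + 9.6r. Reduction in standard error: 1 − √(38.4/n).

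| r | n | Still missing | SE reduction | Power, f = 0.26, ρ = 0.5 |
|---|---|---|---|---|
| 0% | 38.4 | 20% | 0% | 0.88 |
| 25% | 40.8 | 15% | 3.0% | 0.90 |
| 50% | 43.2 | 10% | 5.7% | 0.92 |
| 75% | 45.6 | 5% | 8.2% | 0.93 |

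At r = 10%, n = 39.36 and the reduction is 1.2%. For r = 0% and 50%, power is 0.76 and 0.81 at ρ = 0.3, and 0.98 and 0.99 at ρ = 0.7. At ρ = 0.3, however, the plan's own MNSI total would have been 44, not 32.

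**Step 4: effect on bias.** Suppose that in one arm the 20% missing differ from completers by 0.5 SD (assumed). Taking completers as zero, the true arm mean is 0.20 × 0.5 = 0.10 SD, so a completers-only mean is off by 0.10 SD.
- Half return forms and are typical of the missing: observed mean (0.10 × 0.5)/0.90 = 0.056, so the bias is 0.10 − 0.056 = 0.044 SD, a little under half.
- Half return forms but resemble completers: the other 10% must then differ by 1.0 SD, and the bias stays at 0.10 × 1.0 = 0.10 SD.

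**Step 5: worst-case bounds.** With missing fraction q in each arm, the bounds on the 0–13 group difference have width 2 × 13 × q: 5.2 points at 20% and 2.6 points at 10%. This narrowing does not depend on who responds.

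**The case against.** The strongest case on the other side is that this is a design preference. Nothing in the plan is contradictory or miscalculated here, and one laboratory with two blinded assessors standardises the setting. Several parts of that case stand:

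- **Power.** A reader might infer that the MNSI comparison is underpowered after dropout. The documents do not support this. Ankle ROM set the total, and MNSI power with 38 patients is 0.88 at the correlation that reproduces the plan's figures.
- **Reach.** A reader might infer that all of the 20% could be recovered. The SAP speaks of dropout, which includes patients who leave for good, and does not separate them from those who only miss a visit. The benefit could be near zero.
- **Bias.** A reader might infer that recovering half the forms halves the bias. Step 4 shows that this needs responders to resemble the other missing patients.
- **The second primary outcome.** The severity score also needs monofilament and tuning-fork tests, so it stays missing. A returned MNSI would not help under mean imputation, which uses no other variable.
- **Existing contact.** The documents do not say that the weekly calls continue to T16, and the monitoring calls are made by the unblinded researcher. The remedy should not lean on them.
- **Unseen text.** All procedures follow an Operational Procedure Manual that was not among the documents. It may provide a remote route, so the gap is established only for the protocol and SAP.

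The cost argument does not stand. A home-completed form may carry a setting effect, and home completion may be uneven between arms. But the form would replace a missing value, not a laboratory one, and an analysis without these forms shows how much they matter.

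**Conclusion.** The point holds as a low-cost improvement to the design, not as an error in it. As written, a patient who remains in the trial but misses T8 or T16 contributes no MNSI value at that visit, and the SAP imputes one. At the plan's 20% loss, this can affect at most about 10 of 48 patients per visit.

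The benefit is fewer imputed primary values and less exposure to attrition bias. Its size is uncertain: a standard-error reduction of 0% to 8% for assumed returns of 0% to 75%, and a fall in bias only to the extent that those returning forms are like the other missing patients. The power figures assume a correlation of 0.5. The conclusion covers the MNSI only.

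**What to change.** Amend Study Setting so that a patient in either arm who misses T8 or T16 and has not withdrawn consent is sent the same MNSI form, on paper or electronically. Reconcile the blinding section and Outcomes and measures, which at present give every assessment to Researchers #4 and #5. The amendment should state that:

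- the form is labelled with the study code only and repeats the existing instruction not to disclose allocation;
- a named role sends it, given that the key to the codes is restricted;
- it is returned to a blinded assessor (Researcher #4 or #5) and is not completed by telephone with Researcher #3;
- home-completed values are flagged and included in the intention-to-treat analysis, and the MNSI analysis is repeated without them.

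If the Operational Procedure Manual already covers this, the protocol should say so.

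The cost is a short amendment, about ten forms per visit at the planned dropout rate, and one extra analysis. The downside is that a few forms are completed at home, so a setting effect is possible. The flag and the repeat analysis are there to check for it.

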## **Participants and recruitment**

This study is currently recruiting patients (study start date: May 1, 2019) with a medical diagnosis of DM and DPN from the Department of Endocrinology of the Hospital das Clínicas of the School of Medicine of the University of São Paulo. Forty-eight participants with DPN will be recruited. The potential subjects will be interviewed by telephone and, once selected, assessed in the laboratory to confirm all eligibility criteria. This first laboratory assessment will represent the baseline condition (blind assessment).

The inclusion criteria are adults up to 65 years of age of either sex diagnosed with DM type 1 or 2 with at least mild DPN confirmed by a fuzzy logic-based system [13], who are able to walk independently for at least 10 m, and who do not have more than one amputated toe (that is not the hallux). The exclusion criteria are the presence of an ulcer not healed for at least 6 months and/or active ulcer; a history of surgical procedure to the knee, ankle, or hip or indication of surgery throughout the intervention period; arthroplasty and/or orthosis of lower limbs or indication of lower limb arthroplasty throughout the intervention period; diagnosis of other

neurological disease outside of DM consequences; dementia or inability to give consistent information; receiving any physiotherapy or offloading devices throughout the intervention period; having major vascular complications and/or severe retinopathy; or having a score of 12–21 (probable depression) on the Hospital Anxiety and Depression Scale (HADS).

### **Randomization, allocation, and blinding**

The randomization schedule will be prepared using Clinstat software (University of York, UK) [50] by an independent researcher (Researcher #1) unaware of the numeric codes for the CG and IG groups. The numerical sequence will be kept in opaque envelopes, numbered sequentially, following an order generated by the software. The randomization procedure will follow the instructions of [51]. This sequence will be kept private and stored in a location inaccessible to blind assessors.

After receiving the patients' informed consent to participate, the random allocation to either the IG or CG will be made by another independent researcher (Researcher #2), who will also be unaware of the codes. Only the main research (Researcher #3) responsible for intervention training will know the group allocation of participants. Patients are aware of the treatment, thus not blind to the allocation. Researcher #3 will also be responsible for monitoring the intervention through weekly telephone calls and by checking the table in the booklet monthly. All patients' personal data will be kept confidential before, during, and after the study by encoding participants' names. Only the main researcher and the person receiving treatment will be aware of the meaning of each code. Patients will be allocated to study groups a maximum of one week after baseline evaluation.

The envelope with the initially generated numerical sequence will then be opened, signed, and dated by the independent researcher, who will make the allocation (Researcher #2). Two other researchers (Researchers #4 and #5), which will also be blind to treatment allocation, will be responsible for all clinical, functional, and biomechanical outcome assessments.

To guarantee the blindness of the researchers, before each evaluation, patients will be instructed not to reveal whether they are in the CG or IG; their questions should be asked only for the main researcher (Researcher #3). All researchers will be blind to the block size used in the randomization procedure. The trial statistician will also be blind to treatment allocation until the main treatment analysis has been completed.

### **Treatment arms**

#### **Control**

CG patients will not receive any specific intervention other than the treatment recommended by the health care team, which will include pharmacological treatment and self-care guidelines following the International Working Group on the Diabetic Foot guide [52]. These self-care guidelines have been adjusted for our setting in Sao Paulo and include (1) instructing patients to inspect their feet and inside of shoes daily, wash feet daily (with careful drying, particularly between toes), avoid using chemical agents or plasters to remove calluses or corns, avoid cutting calluses or blisters without supervision, use emollients to lubricate dry skin, and cut toe nails straight across; (2) instructing patients to use socks without elastic and sewing; (3) instructing patients to avoid walking barefoot or wearing shoes without socks or slippers and to seek medical assistance whenever identifying problems in their feet; and (4) providing education

aimed at improving footcare knowledge and behavior as well as encouraging the patient to adhere to this footcare advice. These guidelines will be maintained for both groups. Patients in this group will also receive a weekly telephone call to check the adherence to the care recommended by the medical staff and the foot care guidelines and to avoid the nocebo effect.

## **Intervention**

IG patients will receive an educational booklet with two parts. The first part includes educational information to guide the individuals to change their health behavior regarding autonomous footcare, with information about DPN, footwear, and benefits of exercising the foot-ankle. The second part includes a home-based physiotherapeutic foot-related exercise program comprised of six exercises.

Before starting the exercises protocol, the patients will be instructed by the main researcher on how to perform the exercises using the booklet. The first session will be supervised at the outpatient clinic of the Department of Endocrinology of the Hospital das Clínicas, providing a reliable therapeutic environment for the first intervention.

The exercise program includes strengthening of the intrinsic foot muscles and the extrinsic foot-ankle muscles, and it consists of the following steps:

- (1) Warm-up: The patients will warm up the foot-ankle with three exercises. They will be instructed to massage their feet, and then use a spiky ball to do a deep tissue massage, and subsequently perform rotating movements in each toe, one by one. Altogether, these exercises should be performed within 2–3 minutes.

(2) A total of six exercises will be performed: four exercises for the intrinsic foot muscles and two for the extrinsic foot-ankle muscles. The exercises will be performed in the order suggested by the booklet using objects such as cotton, pencil, balls, and chairs. The interphalangeal, metatarsophalangeal, and ankle joints are targeted in the protocol. The following muscle groups are targeted in protocol: medial-plantar aspect (abductor hallucis, flexor hallucis brevis, and adductor hallucis), lateral-plantar aspect (abductor digiti minimi, flexor digiti minimi brevis, and opponens digiti minimi), middle-plantar aspect (flexor digitorum brevis, quadratus plantae, lumbrical muscles, plantar interosseous, and dorsal interosseous muscles), and dorsal-foot aspect (extensor digitorum brevis and extensor hallucis brevis).

The foot-related exercises will first be performed in the sitting position in one set with 30 repetitions. If the patient finds this too easy, the exercise will then be performed in the standing position, and then standing on one foot. The patient can also increase the number of sets. Patients will follow the exercise program from the booklet with instructions for each exercise prescribed, and after each task, they will fill out a table stating the perceived effort for each exercise (using a Likert scale). At the end of each exercise, patients will define their effort using a visual analogue scale (VAS). If the effort is between 0 and 5, the individual should progress to the next level of the exercise (e.g., from sitting to standing, or using a different object) for the next session. If the effort is between 6 and 8, the same volume and level of difficulty should be maintained. If the effort is between 9 or 10, the amount of repetitions should be decreased or

the position in which the exercise is performed should be modified (e.g., from standing to sitting) (see Additional File 1).

Patients will follow this regime three times a week for 8 weeks, for a total of 24 sessions. The duration of a session should be no longer than 30 minutes. The perceived effort scale will be used to regulate each patient's individual effort for his/her progression to the next session of exercises, and it will be recorded by the participant using the monthly table in the booklet (see Additional File 1).

The discontinuation criteria for the exercises include cramps, moderate to intense pain, fatigue, or any other condition that exposes the patient to any discomfort. The other discontinuation criterion for the intervention is the occurrence of a foot ulcer as assessed by a blinded podiatrist nurse specializing in diabetic feet. The patients will be advised to report any sign of tissue damage to Researcher #3.

